12.4. Treatment and Follow-Up of AEs

Appropriate measures should be taken to treat AEs as necessary, and the response of the study subject should be monitored and recorded. Clinical, laboratory, and diagnostic measures should be obtained as needed, and the results of which should be recorded in the subject's source documentation and transcribed onto the appropriate CRF page.

All SAEs will be followed until resolution, stabilization of the condition, the event is otherwise explained, or the subject is lost to follow-up.

12.5. Serious Adverse Events (SAEs)

An AE is considered serious if it meets one or more of the following criteria:

- Results in death
- Is life-threatening (i.e., a subject is at immediate risk of death at the time of the event, not an event where occurrence in a more severe form might have caused death)

b Rechallenge is when a medication suspected of causing an AE in a specific subject in the past is readministered to that subject. If the AE recurs upon exposure, this is termed a positive rechallenge. If the AE does not recur, this is termed a negative rechallenge.

- Requires inpatient hospitalization or prolongation of existing hospitalization
- Results in persistent or significant disability/incapacity
- Results in a congenital anomaly/birth defect
- Is another important medical event (see below).

Important medical events that do not result in death, are not life-threatening, or do not require hospitalization may be considered SAEs when, based on appropriate medical judgment, they may jeopardize the subject and may require medical or surgical intervention to prevent one of the outcomes listed above. Examples of such medical events include allergic bronchospasm requiring intensive treatment in an emergency room or in a physician's office, blood dyscrasia or seizures that do not result in inpatient hospitalization, and the development of drug dependency or drug abuse. A distinction should be drawn between serious and severe AEs. Severity is a measure of intensity whereas seriousness is defined by the criteria above. For example, a mild degree of gastrointestinal bleeding requiring an overnight hospitalization for monitoring purposes would be considered an SAE, but is not necessarily severe. Similarly, an AE that is severe in intensity is not necessarily an SAE. For example, alopecia may be assessed as severe in intensity, but would probably not be considered an SAE.

12.5.1. SAE Reporting Requirements

The PI or an authorized delegate is responsible for faxing the requested information to the Sponsor or designee within 24 hours or as soon as possible after learning of the event. Following the end of the subject's participation in the study, the PI or an authorized delegate should report SAEs "spontaneously" if considered at least possibly related to study medication.

Notification should be made by emailing a completed SAE Report Form to the Sponsor. Study sites in the US should email a completed SAE Report Form to [contact]. As a minimum requirement, the initial notification should provide the following information:

- Study number
- Subject number
- Gender
- Date of birth
- PI's name and full study site address
- Details of SAE
- Criterion/criteria for classification as "serious"
- Study medication name, or code if blinded, and treatment start date
- Date of SAE onset
- Causality assessment (if sufficient information is available to make this classification).

Initial reports of SAEs must be followed later with detailed descriptions, including clear photocopies of other documents as necessary (e.g., hospital reports, consultant reports, autopsy reports, etc.), with the study subject's personal identifiers removed. All relevant information obtained by the PI or an authorized delegate through review of these documents will be recorded on the AE eCRF page and/or a new SAE Report Form and faxed to the Sponsor or designee within 24 hours of receipt of the information. If a new SAE Report Form is faxed, the PI must sign and date the form. The Sponsor may also request additional information on the SAE, which the PI or an authorized delegate must fax to the Sponsor or designee within 24 hours of the request using a new SAE Report Form, bearing the PI's signature and date.

Any AE fulfilling the criteria for expedited reporting will be reported by the Sponsor to regulatory authorities and Investigators and IEC(s) in accordance with the Sponsor's standard operating procedures (SOPs) and local regulatory requirements.

PIs should report all Investigational New Drug Application safety alerts received from the Sponsor to their local IRB/IECs.

12.6. Guidance for Overdose

There is no clinical experience with MN-001 overdose in humans and there is no available specific antidote to the effects of MN-001. Standard symptomatic support measures should be used in the case of excessive pharmacological effects or overdose.

12.7. Reporting and Follow-up of Pregnancies

If any study subject or subject's partner becomes pregnant after receiving the first dose of study medication (MN-001) and until the follow-up period specified in the protocol, the PI or an authorized delegate should submit a Pregnancy Report Form to the sponsor within 24 hours of the PI or an authorized delegate first becoming aware of the pregnancy. If a pregnancy is to be terminated, the anticipated date of termination should also be provided in the "Additional Information/Comments" field of the Pregnancy Report Form. If a maternal SAE is reported for the study subject during the initial notification of pregnancy, a separate SAE Report Form should also be completed and submitted to the sponsor within 24 hours of the PI or an authorized delegate first becoming aware of the SAE.

Subjects who become pregnant while in the study should be followed for the duration of their pregnancy. If the pregnancy is discovered between regularly scheduled study visits, subjects should return for an unscheduled visit to return their study medication. A quantitative β -hCG should be obtained and subjects should be encouraged to return for follow-up visits. If follow-up visits are not possible, then the principal investigator should collect information about the pregnancy such as spontaneous or elective termination, details of birth, and presence or absence of birth defects, congenital abnormalities, or maternal and newborn complications.

The Sponsor will request that the PI follow the progress of the study subject's pregnancy with the doctor medically responsible for the pregnancy. A new Pregnancy Report Form should be submitted within 24 hours of the PI or an authorized delegate first becoming aware of any new information.

If additional information on the outcome of the pregnancy and/or the details of the birth/delivery is received "spontaneously" by the study site, the PI or authorized delegate should also submit a Pregnancy Report Form within 24 hours of becoming aware of the information. If the outcome of the pregnancy is reported as premature birth, or as elective termination due to a medical reason or as spontaneous or accidental miscarriage, the details of the outcome should be described in the "Additional Information/Comments" field of the Pregnancy Report Form. The pregnancy outcome will generally be reported as a follow-up report.

Complete an SAE Report Form if the delivery outcome meets the criteria for a SAE (e.g., congenital anomaly/birth defect, stillbirth, some other sickness, etc.). The SAE Report Form should be completed with the study subject's details (e.g., subject number, initials, date of birth, investigational product information, etc.) and the details of the fetal SAE and maternal complications should be described in the "Narrative" field of the SAE Report Form.

If a pregnancy is reported for the study subject's partner, the sponsor will provide instructions on how to collect pregnancy information in accordance with local requirements.

12.8. Preplanned Hospitalizations or Procedures

During the study, if a subject has a hospitalization or procedure (e.g., elective surgery) that was scheduled prior to the subject entering the study (i.e., before the subject signed the ICF) for an event/condition that occurred before the study, the hospitalization is considered a therapeutic intervention and not the result of an SAE. However, if the event/condition worsens during the study, it must be reported as an AE or SAE (if the event/condition results in a serious outcome such as prolongation of hospitalization.)

13. STATISTICS

The Statistical Analysis Plan (SAP) will provide comprehensive details on the statistical methods planned for this study.

13.1. Data Analysis

13.1.1. Analysis Populations

Full Analysis Set (FAS) will include all enrolled subjects who receive at least one dose of study medication, and have at least one post efficacy assessment.

Safety Analysis Set will include all subjects who received at least one dose of study drug and had at least one post dose safety assessment.

13.1.2. Statistical Analysis Plan

A statistical analysis plan will outline the efficacy analysis and safety analysis prior to database lock.

13.1.3. Sample Size Justification

No prior data are available on which to base assumptions for sample size/power considerations. The results of this pilot study will be used to design future studies, and the sample size of approximately 15 subjects is deemed to be appropriate for this purpose.

13.1.4. Safety Analysis

Safety analyses will be conducted on the Safety Analysis Set.

The incidence of treatment-emergent AEs (TEAEs, defined as AEs occurring from the time of first dose through 7 days after the last dose of study medication), SAEs and AEs leading to discontinuations will be summarized by treatment group. Incidence of TEAEs will also be summarized by severity (mild, moderate, or severe), as well as by relationship to treatment (not related, possibly related, or probably related) and by seriousness.

Changes from baseline in laboratory values will be summarized by treatment groups for continuous variables. Lab shift tables showing incidence of new or worsening clinically significant findings from baseline to the last visit will be displayed by treatment groups. Shift from baseline to the highest lab value, and from baseline to the lowest lab value will also be displayed.

Incidence of out-of-normal-range values and markedly abnormal change from baseline in laboratory safety test variables will be tabulated by treatment group.

Changes in vital signs from baseline to each visit will be summarized by treatment groups.

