8.8.1.4 Follow-up / Laboratory Re-test Visits/ Early termination visit

Follow up clinic visit: Month 13 (\pm 5 days)

- Physical examination
- Body weight
- Vital signs including supine blood pressure, respiratory rate, heart rate, and temperature
- Adverse event review
- Concomitant medication review

Laboratory Re-test visit

Subjects who have clinically significant abnormal lab finding will return for a laboratory re-test visit and will have the following assessments performed:

- Fasting chemistry, hematology, or urinalysis lab, as indicated
- Adverse event review
- Concomitant medication review

Early Termination visit

Subjects who discontinued study medication will undergo the following assessments:

- Physical examination
- Body weight
- Vital signs including supine blood pressure, respiratory rate, heart rate, and temperature
- Adverse event review
- Concomitant medication review
- Patient diary review and collect
- Study drug accountability
- Study drug return
- 12-lead ECG**
- Fasting safety labs chemistry (including CPK, liver enzymes, lipid panel) hematology, and urinalysis labs**
- Urine β-hCG (pre-menopausal females)**
- Blood Sample for biomarker**
- Pulmonary function test**
- 6MWT**7
- Dyspnea score (MMRC)**
- ATAQ-IPF**
 - ** Assessment need not be performed if prior assessment occurred within 1 month of Early Termination Visit.

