### **10.2.** Definition of Study Phases

Double Blind Treatment Phase (DBT Phase)

The DBT Phase starts with Visit 3 which is the Day 1 of the DBT phase.

The DBT Phase ends with end of the day of Visit 8 (Month 6) and assessments taken on this visit will be considered as belonging to the DBT phase.

Open Label Extension Phase (OLE Phase)

The OLE Phase starts on the following day of Visit 8 and ends with Visit 14(Month 13).

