### 14.3. Clinical Laboratory Evaluations

For numerical lab measurements values below the lower detection limit or above the upper detection limit (indicated in the database as  $\langle xx, \rangle xx, \rangle xx$ ) will be replaced by the detection limit (i.e. xx). Measurements resulting in negative numbers will be set to missing.

Descriptive statistics of measurements will be presented for clinical laboratory values, by treatment arm, phase and visit. Descriptive statistics of changes from baseline will be presented for clinical laboratory values, by treatment arm, phase, and visit.

Categorical lab measurements will be tabulated by treatment arm and visit.

Parameters will be grouped as:

- Blood Chemistry Tests
- Haematology tests
- Urinalysis Tests

Lab shift tables presenting the incidence of new or worsening clinically significant findings from baseline to the last visit will be displayed by treatment arm, for DBT and OLE phase respectivel. For this, a shift table will be created by phase, treatment arms and parameters with the following categories: "CS Low", "NCS Low", "Normal", "NCS High".

Shift from baseline to the highest lab value, and from baseline to the lowest lab value will also be displayed, for the DBT and OLE periods respectively. To create this shift table, change from baseline to the highest and lowest values will be calculated for every subjects within DBT and OLE periods, respectively. Descriptive statistics of these change from baseline values will be presented by phase, treatment arms, parameter and change from baseline category (Cfb to lowest, Cfb to highest). A bysubject listing of these change fom baseline values will be provided.

Incidence of out-of-normal-range values and markedly abnormal change from baseline in laboratory safety test variables will be tabulated by treatment arm and phase. A markedly abnormal change from baseline value is defined as any value larger than three times the upper normal limit.

Laboratory values that are outside the normal range, and their clinically significance will be flagged in the data listings. A by-subject listing of all subjects with abnormal laboratory values will be provided.

Statistical Analysis Plan v1.0

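### The only laboratory shift table by clinical-significance category looks at the last visit of each phase, so findings that clear earlier are absent from a table labelled incidence

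*Protocol*

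**What the plan says.** Protocol 13.1.4 plans the table in these words: "Lab shift tables showing incidence of new or worsening clinically significant findings from baseline to the last visit will be displayed by treatment groups". SAP 14.3 adopts the same label, "Lab shift tables presenting the incidence of new or worsening clinically significant findings from baseline to the last visit", and applies it to each phase: "findings from baseline to the last visit will be displayed by treatment arm, for DBT and OLE phase". It builds the table on the investigator's judgement: "a shift table will be created by phase, treatment arms and parameters with the following categories", the categories being clinically significant (CS) or not, low or high, and normal.

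Three further laboratory outputs are planned.
- **Highest and lowest value.** Protocol 13.1.4: "Shift from baseline to the highest lab value, and from baseline to the lowest lab value will also be displayed". SAP 14.3 carries this out as numeric change: "Descriptive statistics of these change from baseline values will be presented by phase, treatment arms, parameter and change from baseline category".
- **Out-of-range and markedly abnormal values**, tabulated by arm and phase. SAP 14.3 defines markedly abnormal as a value above three times the upper normal limit.
- **Listings**, in which out-of-range values and their clinical significance are flagged.

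Laboratory samples are scheduled at Months 1, 3 and 6 in the double-blind phase and Months 7, 9 and 12 in the open-label phase (Protocol Table 1, 8.8.1.2 and 8.8.1.3). SAP 10.2 ends the open-label phase at Visit 14 (Month 13), where Table 1 schedules no laboratory tests. Retests are for affected subjects only: "Subjects who have clinically significant abnormal lab finding will return for a laboratory re-test visit" (Protocol 8.8.1.4).

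Separately, Protocol 12.1 counts a CS abnormal laboratory result as an adverse event, and Protocol 11 and SAP 14 plan summaries of laboratory treatment-emergent adverse events (TEAEs).

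**The concern.** Incidence means the proportion of subjects in whom something occurred during a period. The stated rule gives the proportion in whom it was present at the end. The two agree only if every CS finding persists to the last laboratory visit. An early change that settles, on or off drug, drops out of the table.

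Laboratory measures are a named safety endpoint. Protocol 4.2.1 puts earlier exposure at no more than 12 weeks, and this trial runs to 52. With about 15 subjects, one omitted subject visibly changes the table. A reader who takes the label at face value could report no new CS findings while the listings show some.

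**Working it through.** The plan gives no figure for this table, so there is none to reproduce. The check has three parts.

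**1. Which findings can the table miss?** List every combination of scheduled visits at which a subject could have a CS finding on a given parameter, leaving out the empty one.
- Double-blind phase, Months 1, 3, 6: 2^3 − 1 = 7 patterns. Those without Month 6 (Month 1 only, Month 3 only, both): 2^2 − 1 = 3. So 3 of 7 are absent. The open-label phase (Months 7, 9, 12) gives the same count.
- Both phases, last visit taken per phase as in the SAP: 2^6 − 1 = 63 patterns. Those with neither Month 6 nor Month 12: 2^4 − 1 = 15. So 15 of 63 appear in neither phase's table.
- A worst post-baseline rule misses 0 of 63.

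These are counts of patterns, not probabilities. The SAP's split by phase helps: a finding present at Month 6 and gone by Month 12 is still shown in the double-blind table.

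**2. What share might be missed?** The documents give no rate or duration, so these are assumptions: onset uniform over Months 0 to 6, exponential duration with mean *m* months, and all draws attended. A finding is seen at a draw if it lasts from onset to that draw.
- Seen at Month 6: proportional to *m*(1 − e^(−6/*m*)).
- Seen at any draw, which means the first draw after onset (gaps of 1, 2 and 3 months): proportional to *m*[(1 − e^(−1/*m*)) + (1 − e^(−2/*m*)) + (1 − e^(−3/*m*))].
- Share shown by the last-visit table = first ÷ second.

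| Mean duration *m* | Numerator ÷ *m* | Denominator ÷ *m* | Share shown |
|---|---|---|---|
| 1 month | 0.998 | 0.632 + 0.865 + 0.950 = 2.447 | 41% |
| 2 months | 0.950 | 0.393 + 0.632 + 0.777 = 1.802 | 53% |
| 3 months | 0.865 | 0.283 + 0.487 + 0.632 = 1.402 | 62% |

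The limits are one third for very short findings and 100% for permanent ones. A simulation of 1,000,000 onsets gave the same three shares.

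**3. Does another output carry the CS status of a cleared finding?**

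| Output | Limited to last visit? | Carries CS status? |
|---|---|---|
| CS shift table | Yes, per phase | Yes |
| Highest/lowest change | No | No, numeric change only |
| Out-of-range and markedly abnormal | No | No; the three-times-upper-limit rule cannot capture a low value |
| Statistics by visit | No | No |
| Laboratory TEAE tables | No, assigned by start date | Yes, if recorded as an adverse event |
| Listings | No | Yes, as a flag |

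The last-visit table is therefore the only shift table by CS category. A cleared finding keeps its CS status in the TEAE tables, if recorded there, and in the listings.

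**The case against.** The strongest reply is that these findings are counted elsewhere. A CS laboratory abnormality is an adverse event by definition (Protocol 12.1), and all adverse events go on the case report form. SAP 14.1 and 14.1.1 assign TEAEs to a phase by start date and tabulate them by arm, system organ class and preferred term, whether or not the event resolves. The excursion would also show in the out-of-range counts and the highest/lowest changes. With about 15 subjects, the flagged listings can be read in full.

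Most of this stands. A reader might infer that no other planned table counts a cleared CS finding, or that its CS status survives only as a listing flag. The documents do not support either inference, because the TEAE tables are planned.

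The TEAE route is still not a full substitute. It depends on the investigator recording the finding. Protocol 8.8.2.4 to 8.8.2.6 say to capture CS changes in physical examination, vital signs and ECG as adverse events, while the laboratory section (8.8.2.13) only points to the test list. Protocol 12.3 lets a diagnosis replace its component findings. No TEAE table shows the baseline category.

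Two further inferences go too far.
- **Visit 14 as the laboratory last visit.** SAP 10.2 says when the phase ends, not which visit supplies the laboratory value. The last visit with a result is the natural reading.
- **A normal retest overwriting a CS value at Month 12.** This is possible, because neither document says whether a retest counts. Neither document says that it does, and Table 1 gives retests a separate column with no visit number.

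**Conclusion.** The point holds for one table. The only shift table by CS category is labelled incidence but reports status at the last visit of each phase. Findings at Month 1, 3, 7 or 9 that have cleared by then are absent from it, and neither the highest/lowest output nor the out-of-range output restores the CS category.

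That conclusion comes from the wording and visit schedule alone. The 41% to 62% range also rests on assumed uniform onset, exponential durations averaging 1 to 3 months and complete attendance. It should not be read as the share of laboratory safety information that the report would lose, because it makes no allowance for the TEAE tables.

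This is a worthwhile, inexpensive improvement in reporting. It does not show that laboratory safety would go unreported.

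**What to change.** In SAP 14.3, and in Protocol 13.1.4 if that document is amended:
1. Add a shift table from baseline to the worst post-baseline CS category at any scheduled or retest visit in the phase. Present the low and high directions separately and count each subject once per parameter.
2. Keep the last-visit shift, titled as a table of resolution. Define last visit as the last scheduled visit with laboratory results in the phase: Month 6, Month 12 or early termination. Visit 14 has no scheduled laboratory tests.
3. State that retests do not replace the scheduled value in the last-visit table.
4. Check that the table shell has a CS category in both directions. The SAP list as read has none for high values, which may only be a loss in reading the PDF.

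**Cost.** One more table and a few lines of SAP text. The values and CS flags are already collected, and the SAP change alone would suffice. Some transient abnormalities unrelated to drug will appear. In the open-label phase there is no placebo arm against which to judge them.

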7.2.2. Exclusion Criteria

- Expected to receive a lung transplant within 1 year from the start of the Treatment Phase or on a lung transplant waiting list at the start of the Treatment Phase.
- Known explanation for interstitial lung disease
- Subjects on OFEVTM (Nintedanib) with dose interruption due to significant adverse events within 6 weeks of screening visits.
- Ongoing IPF treatments with investigational therapy
- Ongoing IPF treatment with Esbriet® (Pirfenidone)
- Immunosuppressants (i.e., Mycophenolate, Imuran, Cyclophosphamide), and cytokine modulating agents within 1 month of Screening Visit and throughout the study
- Use of antibiotics and systemic steroids due to IPF exacerbation within 1 month of Screening Visit
- Clinically significant cardiovascular disease, including myocardial infarct within last 6

- months, unstable ischemic heart disease, congestive heart failure or angina
- Resting pulse < 50 bpm, SA or AV block, uncontrolled hypertension, or QTcF > 450 ms
- Immune system disease
- Any significant laboratory abnormality which, in the opinion of the Investigator, may put the subject at risk
- History of malignancy < 5 years prior to signing the informed consent, except for adequately treated basal cell or squamous cell skin cancer or in situ cervical cancer.
- History or evidence of drug or alcohol abuse
- History of HIV (human immunodeficiency virus) or other active infection.
- Currently has a clinically significant medical condition including the following: neurological, psychiatric, metabolic, hepatic, hematological, pulmonary (other than IPF), cardiovascular (including uncontrolled hypertension), gastrointestinal, urological disorder, or central nervous system (CNS) infection that would pose a risk to the subject if they were to participate in the study or that might confound the results of the study.

Note: Active medical conditions that are minor or well-controlled are not exclusionary if, in the judgment of the Investigator, they do not affect risk to the subject or the study results. In cases in which the impact of the condition upon risk to the subject or study results is unclear, the Medical Monitor should be consulted.

- CYP2C8 and CYP2C9 substrates with narrow therapeutic indices (i.e., paclitaxel, phenytoin and S-warfarin) within 14 days of Screening Visit and throughout the study.
- Macrolide or quinolone class antibiotics within 14 days of Screening Visit and throughout the study.

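### The out-of-normal-range laboratory table takes no account of baseline, so pre-existing or carried-over abnormalities count as incident and, in the double-blind phase, dilute any difference between arms

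*Protocol*

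**What the plan says.** **The table.** Protocol 13.1.4 plans it by treatment group: "Incidence of out-of-normal-range values and markedly abnormal change from baseline in laboratory safety test variables will be tabulated by treatment group". SAP 14.3 plans it by arm and phase: "Incidence of out-of-normal-range values and markedly abnormal change from baseline in laboratory safety test variables will be tabulated by treatment arm and phase". Neither sentence limits the out-of-range count to subjects in range at baseline, or to values that are new or worse.

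**The companion item.** SAP 14.3 explains its second half: "A markedly abnormal change from baseline value is defined as any value larger than three times the upper normal limit". Despite its name, this is an absolute threshold that does not use the baseline value.

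**Entry.** Protocol 7.2.2 excludes "Any significant laboratory abnormality which, in the opinion of the Investigator, may put the subject at risk". Inclusion criterion 7.2.1 also asks for a stable condition, judged in part on screening laboratory results. Another exclusion covers clinically significant metabolic, hepatic or hematological conditions that pose a risk or might confound the results. None of these requires every value to be within range.

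**Baseline and phases.** SAP 14 analyses safety separately for the double-blind and extension phases. SAP 10.3 resets the extension baseline to Visit 8 for former-placebo subjects and gives none for subjects continuing MN-001.

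**Related outputs.** Protocol 13.1.4 plans a shift table: "Lab shift tables showing incidence of new or worsening clinically significant findings from baseline to the last visit will be displayed by treatment groups". Both documents plan a comparison of baseline with the highest and the lowest value. SAP 14.3 delivers it as a summary of changes: "Descriptive statistics of these change from baseline values will be presented by phase, treatment arms, parameter and change from baseline category". SAP 14.3 also plans change from baseline by visit, a by-subject listing of the changes to highest and lowest, and a by-subject listing of abnormal values.

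**The concern.** Incidence should mean events that begin during observation among people who did not have them at the start. A subject who enters with a mildly raised value and keeps it would appear in this table exactly like a subject who becomes abnormal on drug. Under the SAP's by-phase version, a subject on MN-001 who becomes abnormal in the double-blind phase and stays so would appear again as an extension-phase case.

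Laboratory treatment-emergent events are a named safety assessment (Protocol 11), and the pilot is meant to inform later studies (Protocol 13.1.3). Of the planned summary tables, this one comes closest to showing how often results leave the normal range at any time on drug. It should therefore answer that question.

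**Working it through.** The documents give no laboratory abnormality rate, baseline prevalence or power figure, so there is no stated number to reproduce. The check has two parts.

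**1. Does another planned summary table supply the missing count?** The count needed is the number of subjects in range at baseline who are out of range at least once in the phase.

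| Planned output | Uses baseline? | Any time in phase? | Counts new abnormalities? |
|---|---|---|---|
| Out-of-range table | No | Not restricted to one visit | No, mixes old and new |
| Above three times the upper limit | No | Not restricted to one visit | No |
| Shift table | Yes | No, last visit only | Yes, at that visit |
| Change to highest/lowest | Yes | Yes | No, descriptive statistics of change |
| Change from baseline by visit | Yes | By visit | No, descriptive statistics |
| By-subject listings | In part | Yes | No, reader must derive it |

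The shift table misses an abnormality that appears at Month 1 or 3 and resolves before the last visit. No summary table fills the gap.

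**2. How large is the dilution in the double-blind phase?**

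Inputs:
- *b*, the proportion out of range at baseline: assumed 10%, 20% or 30%, equal in the two arms in expectation because of randomization.
- *r*, the true risk of a new abnormality: assumed 30% on MN-001 and 10% on placebo.
- Every baseline abnormality is assumed to persist.

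Displayed rate = *b* + (1 - *b*)*r*. The *b* term cancels between arms, so displayed risk difference = (1 - *b*) × (0.30 - 0.10).

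| *b* | MN-001 | Placebo | Risk difference | Ratio |
|---|---|---|---|---|
| 0 | 30% | 10% | 20 points | 3.00 |
| 10% | 0.10 + 0.90 × 0.30 = 37% | 0.10 + 0.90 × 0.10 = 19% | 18 points | 1.95 |
| 20% | 0.20 + 0.80 × 0.30 = 44% | 0.20 + 0.80 × 0.10 = 28% | 16 points | 1.57 |
| 30% | 0.30 + 0.70 × 0.30 = 51% | 0.30 + 0.70 × 0.10 = 37% | 14 points | 1.38 |

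The ratio falls faster than the difference because a common amount is added to both arms. If only a fraction *s* of baseline abnormalities persists, and the remaining subjects carry the same new-abnormality risk as everyone else, *b* is replaced by *bs* and the dilution is smaller.

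**The case against.** The strongest reply is that this is one descriptive table in an unpowered pilot of about 15 subjects. Other outputs refer to baseline, and at this size a reader can see from the listings who was abnormal before dosing. Much of that stands, and it limits the point. Several stronger readings are tempting and not supported.

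- **That no laboratory output uses baseline.** Not so: the shift table, the changes by visit and the highest/lowest changes all do. What is missing is one specific count.
- **That the table manufactures a drug effect.** With 10 v 5 subjects (15 at 2:1) and no drug effect, the chance that baseline-abnormal proportions differ by at least 20 points either way is 35%, 49% or 56% at 10%, 20% or 30% prevalence. MN-001 is higher by that much in only 16%, 26% or 28%. These figures reflect small arms. A baseline-conditioned table with common new-abnormality rates of 10%, 20% or 30% in 10 v 5 subjects gives the same chances. If conditioning left 8 v 4 (assumed), they would still be 30.0%, 44.5% and 51.1%.
- **That a real effect would be hidden.** The illustration shows attenuation of 2 to 6 points from 20, under full persistence and prevalences that the documents do not supply.
- **That retests inflate the count.** Protocol 8.8.1.4 says "Subjects who have clinically significant abnormal lab finding will return for a laboratory re-test visit". However, neither document says whether retest results enter this table. Nor does either settle whether values or subjects are counted; the once-per-subject rule in SAP 14.1 covers adverse events only. The unit is ambiguous, and inflation is a possibility.
- **That eligibility lets any non-risky abnormality through.** The stability criterion and the exclusions for clinically significant conditions narrow this. Minor out-of-range values can still enter.
- **That carry-over biases the comparison with placebo.** The Protocol sentence mentions no phase, and in the extension every subject takes MN-001, so there is no concurrent placebo contrast to distort. Showing an abnormality in each phase where it is present is a legitimate prevalence display. The fault is calling it incidence.

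**Conclusion.** The concern holds in a limited form. As written, the out-of-range table reports prevalence under the name of incidence. In the double-blind phase it shrinks the expected risk difference by (1 - baseline prevalence): from 20 points to 18, 16 or 14 in the illustration. That size rests on assumed risks of 30% and 10%, assumed prevalences of 10% to 30% and full persistence. The direction, dilution, needs only that some baseline abnormalities persist and that the arms truly differ. In the extension the consequence is that a persisting abnormality is counted again, without a placebo comparison being affected.

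The label on the markedly-abnormal item is a separate, plain mismatch: a change from baseline is defined without baseline. Neither fault touches the efficacy conclusions. The change is worth making because it is cheap and supplies a count that no other summary table gives.

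**What to change.** In SAP 14.3, with matching wording in Protocol 13.1.4:

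1. **Numerator.** For each parameter, separately for low and high, give the number and percentage of subjects in range at the phase-specific baseline who have at least one out-of-range value after that baseline within the phase. Count each subject once.
2. **Denominator.** Use subjects in range at that baseline.
3. **Phase-specific baseline.** For the double-blind phase, use the last value before first study drug; on the Schedule of Events this is the Visit 2 sample, since no safety laboratory draw is scheduled on Day 1. For the extension, use the Visit 8 pre-dose value for all subjects, including those continuing MN-001. Using the pre-study value in both phases for that group would count a persisting double-blind abnormality again.
4. **Adjacent columns.** Show the number already out of range at baseline and how many of those worsened, so that restricting the main count does not lose worsening in these subjects.
5. **The companion item.** Base the markedly abnormal change on the baseline value, or rename it as a threshold of more than three times the upper limit of normal.

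The cost is wording and programming; the scheduled samples already provide the baseline values. The downside is a smaller denominator for parameters where some subjects start out of range. With 4 rather than 5 placebo subjects at risk, for example, each subject is worth 25 points instead of 20.
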